#### **5.3.5.5 Abnormal Vital Sign Values**

Not every vital sign abnormality qualifies as an AE. A vital sign result must be reported as an AE if it meets any of the following criteria:

- Is accompanied by clinical symptoms
- Results in a change in study treatment (eg, dosage modification, treatment interruption, or treatment discontinuation)
- Results in a medical intervention or a change in concomitant therapy
- Is clinically significant in the Investigator's judgment

It is the Investigator's responsibility to review all vital sign findings. Medical and scientific judgment should be exercised in deciding whether an isolated vital sign abnormality should be classified as an AE.

If a clinically significant vital sign abnormality is a sign of a disease or syndrome (eg, high blood pressure), only the diagnosis (ie, hypertension) should be recorded on the Adverse Event Report eCRF (and Form if appropriate).

Observations of the same clinically significant vital sign abnormality from visit to visit should only be recorded once on the Adverse Event Report eCRF (and Form if appropriate)(see Section 5.3.5.3 for details on recording persistent AEs).

#### **5.3.5.6 Abnormal Liver Function Tests**

The finding of an elevated ALT or AST ( $>3 \times \text{ULN}$ ) in combination with either an elevated total bilirubin ( $>2 \times \text{ULN}$ ) or clinical jaundice in the absence of cholestasis or other causes of hyperbilirubinemia is considered to be an indicator of severe liver injury (as defined by Hy's Law). Therefore, Investigators must report as an AE the occurrence of either of the following:

- Treatment-emergent ALT or AST  $>3 \times \text{ULN}$  in combination with total bilirubin  $>2 \times \text{ULN}$
- Treatment-emergent ALT or AST  $>3 \times \text{ULN}$  in combination with clinical jaundice

The most appropriate diagnosis or (if a diagnosis cannot be established) the abnormal laboratory values should be recorded on the Adverse Event Report eCRF (and Form if appropriate)(see Section 5.3.5.1) and reported to the Sponsor immediately (ie, no more than 24 hours after learning of the event), either as an SAE or an AE of special interest (see Section 5.4.2).

#### **5.3.5.7 Deaths**

All deaths that occur during the protocol-specified AE reporting period (see Section 5.3.1), regardless of relationship to study drug, must be recorded on the Adverse Event Report eCRF and Form and immediately reported to the Sponsor (see Section 5.4.2).

Death should be considered an outcome and not a distinct event. The event or condition that caused or contributed to the fatal outcome should be recorded as the single medical concept on the Adverse Event eCRF and Form. Generally, only one such event should be reported. If the cause of death is unknown and cannot be ascertained at the time of reporting, "**unexplained death**" should be recorded on the Adverse Event eCRF and Form. If the cause of death later becomes available (eg, after autopsy), "unexplained death" should be replaced by the established cause of death. The term "**sudden death**" should not be used unless combined with the presumed cause of death (eg, "sudden cardiac death").

Deaths that occur after the AE reporting period should be reported as described in Section 5.6.

### **5.3.5.8 Pre-existing Medical Conditions**

A pre-existing medical condition is one that is present at the screening visit for this study. Such conditions should be recorded on the General Medical History and Baseline Conditions eCRF.

A pre-existing medical condition should be recorded as an AE only if the frequency, severity, or character of the condition worsens during the study. When recording such events on the Adverse Event eCRF (and Form, if appropriate), it is important to convey the concept that the pre-existing condition has changed by including applicable descriptors (eg, "more frequent headaches").

### **5.3.5.9 Hospitalization or Prolonged Hospitalization**

Any AE that results in hospitalization (ie, inpatient admission to a hospital) or prolonged hospitalization should be documented and reported as an SAE (per the definition of SAE in Section 5.2.2), except as outlined below.

An event that leads to hospitalization under the following circumstances should not be reported as an AE or an SAE:

- Hospitalization for respite care
- Planned hospitalization required by the protocol
- Hospitalization for a pre-existing condition, provided that all of the following criteria are met:
  - The hospitalization was planned prior to the study or was scheduled during the study when elective surgery became necessary because of the expected normal progression of the disease
  - The subject has not experienced an AE

An event that leads to hospitalization under the following circumstances is not considered to be an SAE, but should be reported as an AE instead:

- Hospitalization that was necessary because of subject requirement for outpatient care outside of normal outpatient clinic operating hours

## 5.4 IMMEDIATE REPORTING REQUIREMENTS FROM INVESTIGATOR TO SPONSOR

Certain events require immediate reporting to allow the Sponsor to take appropriate measures to address potential new risks in a clinical trial. The Investigator must report such events to the Sponsor immediately; under no circumstances should reporting take place more than 24 hours after the Investigator learns of the event. The following is a list of events that the Investigator must report to the Sponsor within 24 hours after learning of the event, regardless of relationship to study drug:

- Serious AEs (defined in Section 5.2.2; see Section 5.4.2 for details on reporting requirements)
- Adverse events of special interest (defined in Section 5.2.3; see Section 5.4.2 for details on reporting requirements)
- Pregnancies (see Section 5.4.3 for details on reporting requirements)
- Accidental overdoses or medication errors (see Section 5.4.4 for details on reporting requirements)
- Medical device complaints (see Section 5.4.5 for details on reporting requirements)

The Investigator must report new significant follow-up information for these events to the Sponsor immediately (ie, no more than 24 hours after becoming aware of the information). New significant information includes the following:

- New signs or symptoms or a change in the diagnosis
- Significant new diagnostic test results
- Change in causality based on new information
- Change in the event's outcome, including recovery
- Additional narrative information on the clinical course of the event

Investigators must also comply with local requirements for reporting SAEs to the local health authority and Institutional Review Board/Ethics Committee (IRB/EC).

## **5.4.2 Reporting Requirements for Serious Adverse Events and Adverse Events of Special Interest**

### **5.4.2.1 Events That Occur Prior to Study Drug Initiation**

After informed consent has been obtained but prior to initiation of study drug, only SAEs caused by a protocol-mandated intervention should be reported. The paper Clinical Trial Serious Adverse Event/Adverse Event of Special Interest Reporting Form provided to investigators should be completed and submitted to the Sponsor or its designee immediately (ie, no more than 24 hours after learning of the event), either by faxing or by scanning and emailing the form using the fax number or email address provided to investigators.

### **5.4.2.2 Events That Occur after Study Drug Initiation**

After initiation of study drug, SAEs and adverse events of special interest will be reported until 21 days after the last dose of study drug. Investigators should record all case details that can be gathered immediately (ie, within 24 hours after learning of the event) on the paper Clinical Trial Serious Adverse Event/Adverse Event of Special Interest Reporting Form provided to investigators Adverse Event Report Form and submitting the report, either by faxing or by scanning and emailing the form using the fax number or email address provided to investigators.

Instructions for reporting SAEs that occur 21 days after the last dose of study treatment are provided in Section [5.6](#).

## **5.4.3 Reporting Requirements for Pregnancies**

### **5.4.3.1 Pregnancies in Female Subjects**

Female subjects of childbearing potential will be instructed to immediately inform the Investigator if they become pregnant during the study or within 90 days after the last dose of study drug. A paper Clinical Trial Pregnancy Reporting Form should be completed and submitted to the Sponsor or its designee immediately (ie, no more than 24 hours after learning of the pregnancy), either by faxing or by scanning and emailing the form using the fax number or email address provided to investigators. Pregnancy should not be recorded on the Adverse Event eCRF. The Investigator should discontinue study drug and counsel the subject, discussing the risks of the pregnancy and the possible effects on the fetus. Monitoring of the subject should continue until conclusion of the pregnancy. Any SAEs associated with the pregnancy (eg, an event in the fetus, an event in the mother during or after the pregnancy, or a congenital anomaly/birth defect in the child) should be reported on the Adverse Event eCRF (and Form, if appropriate). In

addition, the Investigator will submit a Clinical Trial Pregnancy Reporting Form when updated information on the course and outcome of the pregnancy becomes available.

#### **5.4.3.2 Pregnancies in Female Partners of Male Subjects**

Male subjects will be instructed through the Informed Consent Form to immediately inform the Investigator if their partner becomes pregnant during the study or within 90 days after the last dose of study drug. A paper Clinical Trial Pregnancy Reporting Form should be completed and submitted to the Sponsor or its designee immediately (ie, no more than 24 hours after learning of the pregnancy), either by faxing or by scanning and emailing the form using the fax number or email address provided to investigators. Attempts should be made to collect and report details of the course and outcome of any pregnancy in the partner of a male subject exposed to study drug. When permitted by the site, the pregnant partner would need to sign an Authorization for Use and Disclosure of Pregnancy Health Information to allow for follow-up on her pregnancy. If the authorization has been signed, the Investigator should submit a Clinical Trial Pregnancy Reporting Form when updated information on the course and outcome of the pregnancy becomes available. An Investigator who is contacted by the male subject or his pregnant partner may provide information on the risks of the pregnancy and the possible effects on the fetus, to support an informed decision in cooperation with the treating physician and/or obstetrician.

#### **5.4.3.3 Abortions**

Any abortion should be classified as an SAE (as the Sponsor considers abortions to be medically significant), recorded on the Adverse Event eCRF and Form, and reported to the Sponsor immediately (ie, no more than 24 hours after learning of the event; see Section [5.4.2](#)).

#### **5.4.3.4 Congenital Anomalies/Birth Defects**

Any congenital anomaly/birth defect in a child born to a female subject exposed to study drug or the female partner of a male subject exposed to study drug should be classified as an SAE, recorded on the Adverse Event Report eCRF and Form, and reported to the Sponsor immediately (ie, no more than 24 hours after learning of the event; see Section [5.4.2](#)).

#### **5.4.4 Reporting Requirements for Cases of Accidental Overdose or Medication Error**

Accidental overdose and medication error (hereafter collectively referred to as "special situations"), are defined as follows:

- Accidental overdose: accidental administration of a drug in a quantity that is higher than the assigned dose
- Medication error: accidental deviation in the administration of a drug

In some cases, a medication error may be intercepted prior to administration of the drug.

Special situations are not in themselves AEs but may result in AEs. All special situations associated with balovaptan, regardless of whether they result in an AE, should be recorded on the Adverse Event Report eCRF and Form and reported to the Sponsor immediately (ie, no more than 24 hours after learning of the event). Special situations should be recorded as described below:

- Accidental overdose: Enter the drug name and "accidental overdose" as the event term. Check the "Accidental overdose" and "Medication error" boxes.
- Medication error that does not qualify as an overdose: Enter the name of the drug administered and a description of the error (eg, wrong dose administered, wrong dosing schedule, incorrect route of administration, wrong drug, expired drug administered) as the event term. Check the "Medication error" box.
- Medication error that qualifies as an overdose: Enter the drug name and "accidental overdose" as the event term. Check the "Accidental overdose" and "Medication error" boxes. Enter a description of the error in the additional case details.
- Intercepted medication error: Enter the drug name and "intercepted medication error" as the event term. Check the "Medication error" box. Enter a description of the error in the additional case details.

For balovaptan and itraconazole, each AE associated with a special situation should be recorded separately on the Adverse Event eCRF and Form. If the associated AE fulfills seriousness criteria, the event should be reported to the Sponsor immediately (ie, no more than 24 hours after learning of the event; see Section 5.4.2). For balovaptan, AEs associated with special situations should be recorded as described below for each situation:

- Accidental overdose: Enter the adverse event term. Check the "Accidental overdose" and "Medication error" boxes.
- Medication error that does not qualify as an overdose: Enter the AE term. Check the "Medication error" box.
- Medication error that qualifies as an overdose: Enter the AE term. Check the "Accidental overdose" and "Medication error" boxes.

As an example, an accidental overdose that resulted in a headache would require the completion of two Adverse Event eCRF pages and forms, one to report the accidental overdose and one to report the headache. The "Accidental overdose" and "Medication error" boxes would need to be checked on both eCRF pages.

#### **5.4.5 Reporting Requirements for Medical Device Complaints**

The Investigator must report all medical device complaints to the Sponsor. The Investigator should document as much information as possible on the IMP Deviation Form, including the product batch number, and forward the form to the Sponsor immediately (ie, no more than 24 hours after learning of the event) (refer to the pharmacy manual for further details). If the medical device results in an AE to the study subject, the event must be reported on the Adverse Event eCRF and Form and

submitted through the electronic data capture (EDC) system. If the event is serious, the Adverse Event eCRF and Form must be completed immediately (ie, no more than 24 hours after learning of the event), as outlined in Section 5.4.2.

## **5.5 FOLLOW-UP OF SUBJECTS AFTER ADVERSE EVENTS**

### **5.5.1 Investigator Follow-Up**

The Investigator should follow each AE until the event has resolved to baseline grade or better, the event is assessed as stable by the Investigator, the subject is lost to follow-up, or the subject withdraws consent. Every effort should be made to follow all SAEs considered to be related to study drug or trial-related procedures until a final outcome can be reported.

During the study period, resolution of AEs (with dates) should be documented on the Adverse Event eCRF (and Form, if appropriate) and in the subject's medical record to facilitate source data verification.

All pregnancies reported during the study should be followed until pregnancy outcome.

### **5.5.2 Sponsor Follow-Up**

For SAEs, adverse events of special interest, and pregnancies, the Sponsor or a designee may follow up by telephone, fax, email, and/or a monitoring visit to obtain additional case details and outcome information (eg, from hospital discharge summaries, consultant reports, autopsy reports) in order to perform an independent medical assessment of the reported case.

## **5.6 ADVERSE EVENTS THAT OCCUR AFTER THE ADVERSE EVENT REPORTING PERIOD**

The Sponsor should be notified if the Investigator becomes aware of any SAE that occurs after the end of the AE reporting period (defined in Section 5.3.1) after the last dose of study drug), if the event is believed to be related to prior study drug treatment. These events should be reported through use of the Adverse Event Report Form. The Investigator should report these events directly to the Sponsor or its designee, either by faxing or by scanning and emailing the paper Clinical Trial Serious Adverse Event/Adverse Event of Special Interest Reporting Form using the fax number or email address provided to investigators.

## **5.7 EXPEDITED REPORTING TO HEALTH AUTHORITIES, INVESTIGATORS, INSTITUTIONAL REVIEW BOARDS, AND ETHICS COMMITTEES**

The Sponsor will promptly evaluate all SAEs and adverse events of special interest against cumulative product experience to identify and expeditiously communicate possible new safety findings to investigators, IRBs, ECs, and applicable health authorities based on applicable legislation.

To determine reporting requirements for single AE cases, the Sponsor will assess the expectedness of these events using the following reference document:

- RO5285119 (Balovaptan) Investigator's Brochure
- Itraconazole Summary of Product Characteristics

The Sponsor will compare the severity of each event and the cumulative event frequency reported for the study with the severity and frequency reported in the applicable reference document.

Reporting requirements will also be based on the Investigator's assessment of causality and seriousness, with allowance for upgrading by the Sponsor as needed.

## **6. STATISTICAL CONSIDERATIONS AND ANALYSIS PLAN**

A statistical analysis plan will be generated by the biostatistics department of PRA and will be finalized prior to database lock.

### **6.1 DETERMINATION OF SAMPLE SIZE**

This is an exploratory study for which no formal statistical hypothesis will be tested, and therefore the sample size is chosen to estimate, with sufficient precision, the CYP3A4 inhibition on balovaptan. Between 14 and 18 subjects will be enrolled, so as to have 14 subjects enrolled on either 5 mg or 10 mg balovaptan to ensure a minimum of 12 completers. The sample size was chosen based on balovaptan within-subject variability (CV%) of around 39% for  $AUC_{0-T}$  and 36% for  $C_{max}$  as obtained from the 12 mg repeat dose in study BP25694. Based on the higher value of 39%, it was estimated that with 12 subjects, the half-width of the 90% CI for the ratio of treatment geometric means of the combination (balovaptan + itraconazole) versus balovaptan alone would be obtained by dividing/multiplying the ratio estimate by a factor of 1.30.

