#### **3.3.2 Rationale for Balovaptan and Itraconazole Dose and Schedule**

##### **3.3.2.1 Balovaptan**

A dose of 10 mg balovaptan has shown statistically significant changes in efficacy parameters in adult patients with ASD and is the current proposed dose for Phase 3 trials in adults. However, it is to be expected that exposure in the presence of itraconazole may increase, based on the effect of itraconazole on the exposure of a

single dose of 12 mg balovaptan (at least 3.1-fold increase in  $AUC_{0-120h}$  and 1.4-fold increase in  $C_{max}$ ).

Therefore, in the current study, the effect of itraconazole on the multiple dose PK of a low dose of 5 mg balovaptan qd will initially be assessed in a sentinel group of 4 subjects, in order to assess whether it will be safe to assess the effect of itraconazole on the higher, clinically relevant dose of 10 mg. Single doses of balovaptan up to 76 mg and multiple doses up to 52 mg qd for 14 days were well tolerated. The mean exposure seen with multiple dosing of balovaptan 52 mg was  $484 \pm 43.1$  ng/mL for  $C_{max}$  and  $5920 \pm 817$  h·ng/mL for  $AUC_{0-T}$ .

Balovaptan is being developed for use in ASD, so it is expected that patients will need to take it for prolonged periods of time, likely for years or for life. Hence multiple dose testing is relevant from a clinical point of view. The multiple dose PK of balovaptan with 14 days of dosing was previously characterized in humans and was found to be time and dose dependent. Accumulation was observed with multiple dosing, and steady state of parent and M3 was observed after approximately 7 days of dosing; the time to steady state has only been evaluated with sparse PK measurements for M2. Population modelling indicates that steady state of parent, M2, and M3 following a dose of balovaptan 10 mg is reached later (after around 10 days). In the presence of itraconazole, an increase in plasma  $T_{1/2}$  from 27 to 80 hours was observed. Based on these observations, the maximum level of DDI due to inhibition of CYP3A4 is expected to be observed with 15 days of coadministration of itraconazole with balovaptan, based on a predicted  $T_{1/2}$  of ~ 80 hours for balovaptan when combined with itraconazole.

In addition, exposure to the metabolite M2 has not been previously characterized with intensive PK sampling after multiple doses in humans, and this will also be achieved in the current design.

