## 6.6 PHARMACOKINETIC ANALYSES

Subjects will be excluded from the PK analysis population if they significantly violate the inclusion or exclusion criteria, deviate significantly from the protocol, or if data are unavailable or incomplete. Excluded cases will be documented together with the reason for exclusion. All decisions on exclusions from the analysis will be made prior to database closure.

Individual plasma concentrations at each sampling timepoint for balovaptan, M2 (as applicable), M3, itraconazole and hydroxy-itraconazole will be presented by listings and descriptive summary statistics by treatment, including means, geometric means, ranges, standard deviations and coefficients of variation. Individual and mean concentration versus time will be plotted on linear and semi-logarithmic scales.

All PK parameters for balovaptan, M2 (as applicable), and M3 will be presented by individual listings and summary statistics by treatment including means, geometric means, medians, ranges, standard deviations and coefficients of variation.

The following balovaptan PK parameters will be estimated:

- $C_{max}$ : Day 10 of Period 1; Day 15 and Day 20 of Period 2
- $AUC_{0-T}$ : Day 10 of Period 1; Day 15 and Day 20 of Period 2
- $T_{max}$ : Day 10 of Period 1; Day 15 and Day 20 of Period 2
- $C_{trough}$ : Day 10 of Period 1; Day 15 and Day 20 of Period 2)
- time to steady state (for balovaptan)

The primary PK parameters are  $C_{max}$  and  $AUC_{0-T}$  for balovaptan, M2, and M3 on Day 10 of Period 1 and Day 20 of Period 2.

A linear mixed model analysis will be applied to analyze the log-transformed primary PK parameters. The model assumes a fixed effect for treatment and a random effect for subject. Estimates of geometric mean ratios together with the corresponding 90% CIs will be derived for the comparisons of the PK parameters as follows:

- balovaptan plus itraconazole (test) vs balovaptan alone (reference)

For itraconazole and hydroxy-itraconazole,  $C_{max}$ ,  $AUC_{0-24h}$ , and  $T_{max}$  will be estimated on Day 5 and Day 20 to evaluate whether adequate levels were reached.

Additional PK parameters may be derived if deemed necessary.

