5.3 Tertiary/Exploratory Objectives

- Relationship between the CYP3A4 genotype, among others, and steady state balovaptan exposure, and the influence of the CYP3A4 genotype, among others, on the effect of itraconazole on balovaptan PK
- The plasma exposure of itraconazole and hydroxy (OH)-itraconazole

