7.0 Overview of Planned Analysis

7.1 Changes from Protocol

There are no changes from the protocol.

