16.2.2.1 Drug-Drug Interaction

The effect of itraconazole on the PK of balovaptan on Analysis Days 10 and 15 will be assessed. A linear mixed effect model will be used to analyze the natural log-transformed C_{max} and AUC_{0-tau} values of balovaptan, M2 and M3. An analysis variable representing the combination of treatment and analysis day (balovaptan alone on Day 10, balovaptan + itraconazole on Day 10, and balovaptan + itraconazole on Day 15) will be used as fixed effect and subject will be used as a random effect. The estimates for the differences between

- 1) balovaptan + itraconazole on Day 15 (test) and balovaptan alone on Day 10 (reference)
- 2) balovaptan + itraconazole on Day 10 (test) and balovaptan alone on Day 10 (reference)

will be back-transformed to derive the geometric mean ratios of balovaptan + itraconazole (on Days 10 and 15) over balovaptan alone on Day 10 together with the corresponding 90% CIs for the comparisons of the PK parameters.

In addition, as an exploratory analysis, the CYP3A4 genotype will be added as a factor. The relationship between other genotypes may also be explored.

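### SAP 7.1 declares no changes, yet SAP 16.2.2.1 changes the model behind the primary 90% CI; separately, the planned precision factor of 1.30 is 1.32 under the Protocol 6.6 model

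*Protocol*

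**What the plan says.** Protocol 6.6 defines the primary parameters as Cmax and AUC over the dosing interval "for balovaptan, M2, and M3 on Day 10 of Period 1 and Day 20 of Period 2". These are analysed on the log scale: "The model assumes a fixed effect for treatment and a random effect for subject". The output is a geometric mean ratio with a 90% CI. The same section plans to estimate Period 2 Day 15 parameters, but does not list them among the primary parameters.

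SAP 16.2.2.1 specifies the fixed effect differently: "An analysis variable representing the combination of treatment and analysis day". It has three levels: balovaptan alone on Day 10, and the combination on Analysis Period 3 Days 10 and 15, which are Study Period 2 Days 15 and 20. Subject is the only random effect and no other covariance structure is named, so I read it as one residual variance for all three levels. Besides the primary contrast, it adds "balovaptan + itraconazole on Day 10 (test) and balovaptan alone on Day 10 (reference").

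SAP 3.0 says the SAP supersedes the protocol's statistical section and that substantial differences will be identified. SAP 7.1 says "There are no changes from the protocol". The SAP Document History records on 14-Nov-2018 that the interaction model was clarified.

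On precision, Protocol 6.1 assumes a within-subject CV of around 39% for AUC and 36% for Cmax. It says that with 12 subjects the 90% CI "would be obtained by dividing/multiplying the ratio estimate by a factor of 1.30". The synopsis and SAP 6.1 repeat this. None of the three gives a formula, a quantile or degrees of freedom.

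**The concern.** The study tests no hypothesis. The 90% CI is its main inferential result, and the width of that interval is the only justification for the sample size. Two things do not line up.

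First, the model that produces the primary interval is not the one in the protocol, and the section meant to record such differences records none. The third record does more than add a secondary comparison: through the pooled residual it also enters the standard error and degrees of freedom of the primary contrast. The nominal level of that interval then rests on an assumption about the similarity of the three records that the two-record analysis does not need.

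Second, the stated factor of 1.30 does not follow from the model in the same protocol.

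**Working it through.** **Inputs.** CV 39% (AUC) and 36% (Cmax), 12 completers and 14 enrolled at the analysed dose, two-sided 90% CI (Protocol 6.1); models from Protocol 6.6 and SAP 16.2.2.1.

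**The precision factor.** Log-scale SD: sqrt(ln(1 + 0.39²)) = 0.3763. Factor: exp[q × 0.3763 × sqrt(2/n)].

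Routes that give 1.30 at n = 12:
- t quantile with 22 df: 1.302
- normal quantile with the SD set equal to the CV: exp(1.645 × 0.39 × sqrt(2/12)) = 1.299

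The documents do not say which route, if either, was used.

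Protocol 6.6 model: df = 12×2 − 12 − 1 = 11, and q = t(0.95, n−1).
- n = 12: exp(0.2759) = 1.318
- n = 13: 1.301
- n = 14: 1.286
- Cmax, CV 36%, n = 12: 1.292
- For 1.30 with 11 df at n = 12, the CV would have to be about 37.0%; CVs of 38.5% to 39.5% give 1.313 to 1.322.

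SAP 16.2.2.1 model: df = 12×3 − 12 − 2 = 22. With equal variances and equal correlation the factor is exp(0.2638) = 1.302. SAP 6.1 therefore agrees with SAP 16.2.2.1 as written. Ratio of log half-widths: 0.2759/0.2638 = 1.046, so the two-record interval is about 5% wider.

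**Coverage of the pooled interval.** Let the residual variance be a on balovaptan alone and b on the combination, and let ρ be the correlation between the two on-itraconazole residuals beyond the subject effect. The pooled mean square has expectation (a + 2b − ρb)/3. The primary contrast needs (a + b)/2. These agree when b(1 − 2ρ) = a. Equal variances with ρ = 0 satisfy this, but so do other combinations. With a = b = σ² the pooled mean square is σ²(1 − ρ/3), which is too small for any positive ρ.

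Simulation with n = 12 and complete data (200,000 runs); ρ and the SD ratio are assumptions:

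| SD ratio, combination/alone | ρ | Pooled 90% CI coverage |
|---|---|---|
| 1 | 0 | 90.0% |
| 1 | 0.25 | 88.5% |
| 1 | 0.5 | 86.6% |
| 1 | 0.8 | 83.7% |
| 0.7 | 0 | 87.9% |
| 1.4 | 0 | 91.5% |
| 1.4 | 0.25 | 89.9% |

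In the four equal-variance rows the pooled factor is 1.302, 1.287, 1.272 and 1.253. The two-record interval is a paired t interval on each subject's log ratio, so its coverage is 90% in every row; with equal variances its factor is 1.318.

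**On the ratio scale.** At the 3.1-fold AUC increase seen earlier after a single dose (Protocol 1.2.1.1), the two-record interval is 3.1/1.318 to 3.1×1.318 = 2.35 to 4.09. The pooled interval at ρ = 0.5 and equal variances is 3.1/1.272 to 3.1×1.272 = 2.44 to 3.94.

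**The case against.** The case for leaving the plan alone has real force. The study is exploratory and states no precision threshold that 1.32 would miss. The CV is given only as around 39%. Thirteen completers out of 14 restore 1.30. The SAP's own model gives 1.30 under the usual planning assumptions. The Day 15 profiles were always planned, the point estimate does not move, and the SAP model was specified before analysis. All of this stands, and it is why the factor is a minor matter.

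It does not rescue SAP 7.1. Changing which records feed the standard error and degrees of freedom of the primary interval is a change, and one that SAP 3.0's own rule covers.

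A reader might go further and infer that the pooled interval is too narrow. The documents do not support that. Positive correlation does not by itself cause under-coverage: at ρ = 0.25 with an SD ratio of 1.4, coverage is about 90%. SAP 5.3 lists "the influence of the CYP3A4 genotype, among others, on the effect of itraconazole on balovaptan PK" as something to explore; it does not say such an effect is expected. Protocol 3.3.2.1 predicts a half-life of about "80 hours for balovaptan when combined with itraconazole", so the two Period 2 profiles, 120 h apart, are separated by 1.5 half-lives. That describes decay of drug present, not the correlation of a subject's deviations in log AUC, and no step in the documents links the two.

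Nor should 1.30 be read as an irreproducible figure, or as one derived from the SAP model: more than one route reaches it.

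**Conclusion.** SAP 7.1 is wrong as written, because SAP 16.2.2.1 changes the model that yields the primary 90% CI. The effect on the interval is conditional. The pooled interval is guaranteed nominal when all three records share one residual variance and are equally correlated; otherwise it can cover too little or too much. Across the assumed values tabulated, coverage runs from about 84% to 91.5%. The documents give neither the correlation nor the variance ratio, so under-coverage is a risk that has not been shown. A conclusion that exposure rises would be unaffected at the ratio used above.

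The factor of 1.30 in Protocol 6.1 and the synopsis should read 1.32 under the Protocol 6.6 model. The difference is small, and the 14 planned subjects absorb it if at least 13 complete.

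The calculations assume normal log-scale errors and complete data.

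**What to change.** 1. **SAP 7.1.** Replace the statement with one saying that Protocol 6.6 specified two records per subject for the primary comparison, and that the SAP adds Analysis Period 3 Day 10 as a third level together with a second contrast.
2. **SAP 16.2.2.1.** Take the primary contrast (Analysis Period 3 Day 15 against balovaptan alone on Day 10) from the Protocol 6.6 two-record model. Alternatively, fit the three-level model with an unstructured within-subject covariance and Kenward-Roger degrees of freedom; with complete data this gives the same interval. Keep the pooled model for the Day 10 contrast or as supportive.
3. **Precision statement.** Give the factor as 1.32 at 12 completers (1.30 at 13, 1.29 at 14) with the formula exp[t(0.95, n−1) × sqrt(ln(1+CV²)) × sqrt(2/n)]. Do this in Protocol 6.1 and the synopsis at any amendment. SAP 6.1 needs it only if step 2 is adopted.

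The cost is a few sentences and one model specification, on data already planned, with no added subjects or samples. The statistical price is 11 instead of 22 degrees of freedom at 12 completers, the roughly 5% wider log half-width shown above. If the sponsor keeps the pooled model as primary, step 1 is still needed.
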